7.3.21.3 Bone Lesion Assessment (Skeletal Survey, CT, or PET/CT)

Skeletal survey will include lateral radiograph of the skull, anteroposterior and lateral views of the spine, and anteroposterior views of the pelvis, ribs, femora, and humeri. Low-dose whole body computed tomography (LD WBCT) or fluorodeoxyglucose-positron emission tomography/computed tomography (FDG-PET/CT) may be used in place of skeletal survey. Bone lesion assessment (all subjects) will be conducted at screening (may be within 30 days prior to randomization) and will be repeated if worsening clinical symptoms suggest PD, or as clinically indicated. The same method of assessment used at baseline will be used throughout the study. These imaging studies will be read locally.

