PD	
 • Increase of 25% from lowest response value in 1 or more of the following: 
 – Serum M-component (absolute increase must be ≥ 0.5 g/dL) and/or – Urine M-component (absolute increase must be ≥ 200 mg per 24 hours) and/or – Only in patients without measurable serum and urine M protein levels: the difference between involved and uninvolved FLC levels (absolute increase must be > 10 mg/dL) – Only in patients without measurable serum and urine M protein levels and without measurable disease by FLC levels, bone marrow plasma cell percentage (absolute percentage must be $\geq 10\%$) • Definite development of new bone lesions or soft tissue plasmacytomas or definite increase in size of existing bone lesions or soft tissue plasmacytomas • Development of hypercalcemia (corrected serum calcium > 11.5 mg/dL or 2.75 mmol/L) attributed solely to the plasma cell proliferative disorder

Page 2 of 2

CR = complete response; FLC = free light chain; MR = minimal response; PD = progressive disease; PR = partial response; sCR = stringent complete response; SFLC = serum free light chain; SPD = maximal perpendicular diameter; VGPR = very good partial response.

All response categories (CR, sCR, VGPR, PR) require 2 consecutive assessments made at any time before the initiation of any new therapy as well as no known evidence of progressive or new bone lesions if radiographic studies were performed.

Radiographic studies are not required to satisfy these response requirements. Bone marrow, plasmacytoma, and skeletal survey assessments are not required to be confirmed by repeat testing.

For sCR: presence/absence of clonal cells is based upon the kappa lambda ratio. An abnormal kappa lambda ratio by immunohistochemistry and/or immunofluorescence requires a minimum of 100 plasma cells for analysis.

If patients do not have measurable disease at baseline, they can only be assessed for at least a CR or progressive disease (PD), otherwise they will be NE.

Determination of PD while on study requires 2 consecutive assessments made at any time (no minimal interval is required, it can be done the same day; however, to confirm response or PD, 2 discrete samples are required) before classification of PD and/or the

institution of new therapy. Confirmative samples for PD after new therapy can be used. Serum M-component increases of ≥ 1 g/dL from nadir are sufficient to define progression if nadir M-component is ≥ 5 g/dL.

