
Plasmacytomas: A definite increase in the size is defined as a $\geq 50\%$ increase from nadir as measured serially by the sum of the products of the maximal perpendicular diameter (SPD) of the measurable lesion or a $\geq 50\%$ increase in the longest diameter of a previous lesion with ≥ 1 cm short axis. A plasmacytoma is considered measurable if the longest diameter is at least 1 cm and the product of the cross diameters is at least 1 cm². Plasmacytomas of lesser size will be considered non-measurable. The requirement for bi-directional measurements applies only to plasmacytomas. The plasmacytoma specifications for PD are based on the sponsor's interpretation of the IMWG-URC and practical considerations for study execution.

For defining nadir, in the case where a value is felt to be a spurious result per physician/Independent Review Committee (IRC) discretion (eg, a possible laboratory error), that value will not be considered when determining the lowest value.

Sources: Durie et al, 2006; Kumar et al, 2016; Rajkumar et al, 2011.

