4.2 Subgroups

In addition to the stratification factors for randomization, the following covariates will be used to examine primary and selected secondary endpoints in subgroups as appropriate. When there is not a sufficient number of subjects in the subgroup (ie, less than 10% of subjects in a treatment arm), relevant subgroups may be combined.

- baseline demographics and characteristics:
 - age (≤ 75 , > 75)
 - sex (female, male)
 - race (white and other categories depending on frequency observed)
 - region (North America, Europe, Asia **Pacific**, Other)
- baseline organ function and comorbid conditions:
 - ECOG PS (0-1, 2)
 - baseline CrCl (15-30, 30-50, 50-80, ≥ 80 mL/min)

- baseline disease characteristics:
 - prior Lenalidomide exposure (yes vs no)
 - refractory to Lenalidomide (yes vs no)
 - prior Bortezomib or Ixazomib exposure (yes vs no)
 - refractory to Bortezomib or Ixazomib (yes vs no)
 - **prior IMiD exposure (yes vs no)**
 - **refractory to IMiD (yes vs no)**
 - revised ISS stage (Stage 1 or 2, Stage 3)
 - IgG vs non-IgG
 - determination of measurable disease at baseline (**based on SPEP only, based on UPEP only or both SPEP and UPEP**, based on SFLC only)
 - β 2-microglobulin level (< 3.5, \geq 3.5 and < 5.5, \geq 5.5 mg/L)
 - risk group as determined by **genetic abnormality per IMWG** (high risk group, standard risk group)
 - presence of soft tissue plasmacytoma (yes, no)

5. Definitions

Baseline

Unless otherwise defined, baseline will be defined as the latest value measured on/before day1 of the first cycle of protocol-specified therapy. The protocol specifies that all study procedures on day 1 should be completed before the initiation of protocol-specified therapy, which will be the assumption in the analysis. If a day 1 value is not available, the latest value before the day of the start of protocol-specified therapy will be used. If a subject doesn't receive any protocol-specified therapy, then the latest value prior to or on randomization date will be used.

For plasmacytoma and skeletal survey, baseline will be defined as the latest assessment from screening period until 7 days after the Day 1 Cycle 1.

Body Surface Area (BSA)

BSA will be calculated using the Mosteller formula (Mosteller, 1987):

$$\text{BSA (m}^2\text{)} = ([\text{Height(cm)} \times \text{Weight(kg)}]/3600)^{1/2}.$$

Complete Response Rate (CRR)

CRR is defined as the proportion of subjects whose best overall response is sCR or CR.

Death Date

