6.3 Per Protocol Set(s)

The per protocol analysis set is a subset of the full analysis set which includes subjects who do not have important protocol deviations that are considered to have an effect on efficacy outcomes. The list of important protocol deviations is maintained by the sponsor on an ongoing basis and will be finalized before the primary analysis of the study. **The Per-protocol Sets are different for OS analysis from PFS/ORR analysis.**

Subjects with the following protocol deviations will be excluded from the per protocol set for OS analysis:

- **PP** - Inclusion criteria of relapsed or progressive multiple myeloma
- **PP** - Inclusion criteria of measurable disease
- **PP** - Inclusion criteria of at least PR to at least 1 prior line of therapy
- **PP** - Inclusion criteria of 1 - 3 prior therapies for multiple myeloma
- **PP** - Inclusion criteria of prior exposure to carfilzomib therapy
- **PP** - Inclusion criteria of prior exposure to anti-CD38 antibody therapy
- **PP** - Exclusion criteria of history of other malignancy within the past 5 years
- **PPD** - Subject received therapy with a marketed or investigational anticancer therapeutic or radiation to large marrow reserves for either a therapeutic or palliative intent prior to confirmed progressive disease
- **PP** - Subject received different treatment type from randomized treatment assignment; subject in arm 2 received daratumumab
- **PP** - Incorrect carfilzomib dose (under dose)

In addition to the deviations listed above, subjects who had the following deviations will also be excluded from per-protocol set for PFS and ORR analyses:

- **PPD** - Subject permanently discontinued treatment due to progressive disease (PD) based on local labs not central labs, except in the case of disease progression based on hypercalcemia
- **PP** - Screening lab disease assessment performed outside window and not reported prior to C1D1 dosing, such that the primary endpoint cannot be assessed

- **PPD** - Failure to obtain extramedullary plasmacytoma assessment and/or bone lesion assessment not carried out within 30 days prior to randomization or not obtained post-randomization and prior to C1D1 such that the primary endpoint cannot be assessed
- **PPD** - Failure to obtain all required response assessments per protocol schedule of assessments and IMWG URC specifications to assess PFS

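### For plasmacytoma and bone lesions, the SAP lets an unscheduled post-dose assessment in the first week replace an existing pre-dose baseline

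*SAP*

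**What the plan says.** SAP section 5 (Definitions, Baseline) contains two rules. In general, "baseline will be defined as the latest value measured on/before day1 of the first cycle of protocol-specified therapy", and procedures on day 1 are assumed to precede dosing. Plasmacytoma and skeletal survey have their own rule: "baseline will be defined as the latest assessment from screening period until 7 days after the Day 1 Cycle 1". It carries no condition that a pre-dose assessment be missing.

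Other places bear on it:

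- **Timing of assessments.** Protocol 7.3.21.3 puts bone lesion imaging at screening for everyone, up to 30 days before randomization. After that it "will be repeated if worsening clinical symptoms suggest PD, or as clinically indicated". Protocol 7.3.21.4 asks for a screening plasmacytoma evaluation only where one is clinically suspected. Both are read or evaluated locally.
- **Use in response criteria.** Under Protocol Appendix M, progression includes "Definite development of new bone lesions or soft tissue plasmacytomas or definite increase in size of existing bone lesions or soft tissue plasmacytomas". Protocol 7.3.21.5 asks for no second assessment when progression is found by imaging. Partial response requires any plasmacytoma present at baseline to shrink by at least half.
- **Per-protocol set.** Among the deviations that exclude a subject from the PFS and ORR per-protocol set, SAP 6.3 lists imaging outside the 30-day window or "not obtained post-randomization and prior to C1D1 such that the primary endpoint cannot be assessed".
- **Use as baseline variables.** SAP 4.2 has a subgroup for presence of soft tissue plasmacytoma. SAP 9.4 tabulates presence of plasmacytoma and of bone lesions at baseline.
- **Declared changes.** SAP section 10 lists only changes to subgroups.

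**The concern.** A baseline should describe the subject before treatment. Here the later assessment wins, even when it follows the first doses and a valid screening assessment exists. Bone imaging after screening is prompted by symptoms or clinical need, so subjects imaged in the first week are selected for possible change, and the person ordering the image knows the arm.

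Two things follow from the wording. A lesion that first appears in that week is absorbed into baseline and is no longer new. And the reference for plasmacytoma shrinkage moves to a value that treatment may already have altered. If the rule feeds the response assessments, it could alter individual progression and response calls. If it does not, it still defines a subgroup and baseline tables partly from post-dose findings.

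**Working it through.** **The plan's own figure.** SAP 3.2 gives 188 events for at least 90% power at HR 0.6, 2:1 allocation, one-sided 0.025. By Schoenfeld's formula, √(188 × 2/9) × |ln 0.6| − 1.96 = 6.464 × 0.5108 − 1.96 = 1.342, which is 91.0% power. This reproduces and is not in dispute; the point concerns a definition.

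**1. What is inside the window.** Seven days after cycle 1 day 1 is day 8. Day 1 itself is treated as pre-dose, so the disputed days are 2 to 8. Protocol Tables 13 and 14 schedule carfilzomib and dexamethasone on days 1, 2 and 8 in both arms, and daratumumab on the same days in KdD.

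**2. Where this sits on the PFS clock.** PFS starts at randomization. The first dose may follow by up to 3 days (Protocol 5.1) or 5 calendar days (SAP section 5, Randomization Date); the two limits differ and need reconciling. Baseline can therefore fall up to 3 + 7 = 10 or 5 + 7 = 12 days into follow-up.

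**3. Is anything scheduled then?** Plasmacytoma is followed every 28 days by examination or every 12 weeks by imaging. Day 29 less the 7-day window is day 22. Bone imaging has no post-screening schedule. An override therefore needs a pre-dose assessment plus an unscheduled one on days 2 to 8.

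**4. Effect on the partial response element** (illustrative sums of products of diameters, not trial data). Take 16 cm² before dosing, 12 cm² on day 7 and 7.5 cm² later.
- Against the pre-dose value: 1 − 7.5/16 = 53.1%, met.
- Against the SAP baseline: 1 − 7.5/12 = 37.5%, not met.
- The threshold moves from 0.5 × 16 = 8 cm² to 0.5 × 12 = 6 cm².

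Early growth moves it the other way. With 4 cm² at screening and 6 cm² by day 8, the threshold eases from 2 to 3 cm².

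**5. Effect on progression.** Growth of an existing plasmacytoma is judged from nadir (Appendix M). In the 4 to 6 cm² case, growth is 6/4 − 1 = 50%. If the screening value is kept as nadir, the progression threshold is 1.5 × 4 = 6 cm² and is reached. If it is dropped, the threshold becomes 1.5 × 6 = 9 cm² and is not. The SAP does not say which applies. A wholly new lesion is the clearer case: once it belongs to baseline it cannot be new.

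**6. Scale.** The documents give no count of subjects with both assessments. Suppose 0.2% to 3% of 450 lost an early progression event this way (an assumption, and only if the IRC applied the rule). That is 0.9 to 13.5 events, or 0.5% to 7.2% of 188. If none were replaced, power would be 90.9% to 88.9% by the same formula. Because the analysis is event-driven, power is not the main issue.

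**The case against.** The strongest reply is that the link to the primary endpoint is missing. The IRC determines PFS and ORR, blinded and under its own charter (Protocol 10.3.2, SAP 9.1), and ORCA has a separate specification (SAP section 5). Neither is in the documents, and nothing says that either takes its baseline from this SAP rule. A reader might infer that the rule removes PFS events or changes ORR; the documents do not support that. This stands in full.

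A reader might also infer that the SAP contradicts itself. It does not, strictly. The general baseline rule allows for definitions made elsewhere, so the lesion rule is an exception. The SAP 6.3 deviation applies only when the primary endpoint cannot be assessed, and only to per-protocol exclusion. What remains is that the exception is broader than a rescue of missing baselines would need.

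On size, the objection is largely right. No scheduled visit falls on days 2 to 8, and many subjects will have no screening plasmacytoma evaluation to override. ORR uses best response, so in the worked case later shrinkage to 6 cm² or less would still meet the element; a difference persists only if the lesion never gets to 6 cm² but does reach 8 cm² or less.

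Finally, an assessment close to the start of treatment has some merit. Screening imaging may be 30 + 3 = 33 days old at first dose under the protocol's limit, and a lesion seen on day 6 may have arisen in that gap. This does not rescue the rule: the PFS clock is already running from randomization, and the rule absorbs post-dose change as well.

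**Conclusion.** The rule should be corrected; its demonstrated reach is limited. As written, a day 2 to 8 assessment replaces a valid pre-dose one for plasmacytoma and skeletal survey. This follows from the text and needs no assumption.

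The certain consequence is that the plasmacytoma subgroup and the baseline lesion tables can rest on post-dose findings. An effect on PFS or ORR is conditional on the IRC or ORCA using the same baseline. For growth of an existing plasmacytoma, it is further conditional on the screening value not being kept as nadir.

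The number affected is unknown and probably small, although for an affected subject the change is categorical. A reader might suspect that the rule favours KdD. The documents do not show this: the same rule applies to both arms, and early shrinkage makes partial response harder to reach while early growth makes it easier.

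**What to change.** Replace the sentence in SAP section 5 with a rule on these lines: for plasmacytoma and skeletal survey, baseline is the latest assessment before first dose; only if there is none, the earliest assessment within 7 days after cycle 1 day 1 is used and flagged.

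Then:
- state that any pre-dose value stays in the nadir and new-lesion comparisons;
- confirm that the IRC charter and ORCA specification apply the same rule, or record where they differ;
- list by arm the subjects whose baseline changes. If derivations have already been run, add a sensitivity analysis under the revised rule.

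The cost is one sentence, one re-derived flag and a short listing. A subject with only a first-week assessment still has a baseline, so no data are lost. The small downside is that a lesion arising between screening imaging and first dose would count as post-baseline; the listing would show how often this could matter.

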For subjects who die during the study, the death date will be recorded on the end of study CRF **page** in the end of study date. If only the day of a death date is missing, death date will be imputed using the following rules: 1) Day 1 of the month will be used to impute if year and month indicate that death happened later than last known alive date; 2) One day after last known alive date will be used to impute if death happened in the same month and year as last known alive date.

The imputed death date will be used in calculation of duration of response, progression-free survival and overall survival.

Duration of Response (DOR)

DOR will be calculated only for subjects who achieve a best overall response of PR or better, ie, sCR, CR, VGPR, or PR. The duration will be calculated in months from the earliest date a response of PR or better is first achieved and subsequently confirmed to the earliest date of confirmed PD or death due to any cause:

$$\text{DOR} = (\text{PD} / \text{death date} - \text{response start date} + 1) / 30.4$$

Subjects will be censored using the same censoring rules for PFS as listed in [Table 1](#) if applicable.

Genetic Risk Group

The **high-risk group consists of** subjects with **the following** genetic abnormalities t(4;14), t(14;16), and/or deletion 17p. The **standard-risk group consists of** subjects **who do not have any of the above genetic subtype**. The **unknown group consists of subjects who cannot be identified as high-risk nor standard-risk**.

International Staging System (ISS) Stage at Baseline

ISS stage at baseline will be calculated using serum beta-2 microglobulin and serum albumin values collected at baseline, based on the criteria published by the International Myeloma Working Group ([Greipp 2005](#)):

Stage I: Serum beta-2 microglobulin < 3.5 mg/L and serum albumin ≥ 3.5 g/dL

Stage II: Serum beta-2 microglobulin < 3.5 mg/L and serum albumin < 3.5 g/dL or Serum beta-2 microglobulin 3.5–<5.5 mg/L irrespective of the serum albumin

Stage III: Serum beta-2 microglobulin ≥ 5.5 mg/L

Revised International Staging System (R-ISS) Stage at Baseline

R-ISS stage at baseline will be calculated using ISS, risk group by FISH, and LDH, based on the criteria published by the International Myeloma Working Group ([Palumbo, 2015](#)):

Stage I: ISS stage I and standard risk group by FISH and normal LDH

Stage II: Not R-ISS stage I or III

Stage III: ISS stage III and {either high-risk group by FISH or high LDH}

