8.3 Handling of Missing and Incomplete Data

The descriptive statistics will identify the extent of missing data. Rules for handling missing data related to endpoints are described in the endpoint definitions or in the description of analyses. The handling of incomplete and partial dates for adverse events and concomitant medications are described in [Appendix A](#).

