9.4 Demographic and Baseline Characteristics

Demographic and baseline disease characteristics will be summarized by treatment group and overall using descriptive statistics for the Full Analysis Set. These include, but are not limited to the following.

- Baseline demographics and characteristics:
 - Age at randomization
 - As continuous variable
 - As categorical variable: <75, ≥ 75 years
 - **As categorical variable: 18 – 64, 65 – 74, 75 – 84, ≥ 85 years**
 - Sex (Male, Female)
 - Race (White and other categories depending on frequency observed)
 - Ethnicity (Hispanic or Latino, Not Hispanic or Latino)
 - **Height (cm)**
 - Weight (kg)
 - Body surface area (m²) (**as continuous in m²; as categorical variable: ≤ 2.2, > 2.2 m²**)
 - Body mass index
 - Region (North America, Europe, Asia **Pacific**, Other)
 - Frailty status (**Fit, Intermediate Fitness, Frail, Not available**)
- Baseline organ function and comorbid conditions:
 - ECOG performance status (0-1 [0, 1], 2)
 - Hemoglobin (g/L) (**as continuous in g/L; as categorical variable: < 105, ≥ 105 g/L**)
 - Absolute Neutrophil Count (**10⁹/L**) (**as continuous in 10⁹/L; as categorical variable: < 1.5, ≥ 1.5 *10⁹/L**)
 - Platelet count (10⁹/L) (**as continuous in 10⁹/L; as categorical variable: < 105, ≥ 105 *10⁹/L**)

- Corrected calcium (mg/dL): calculated **by Covance (central laboratory)** as [serum calcium (mg/dL) + 0.8×(4 - serum albumin (g/dL))] **(as continuous in mg/dL; as categorical variable: ≤11.5, > 11.5 mg/dL)**
- Creatinine clearance (CrCl, **as continuous in mL/min; as categorical variable: < 15, 15 - < 30, 30-<50, 50-<80, ≥80 mL/min**): Measured or calculated CrCl according to the Cockcroft-Gault formula **by Covance (central laboratory)**:

$$CrCL(mL / min) = \frac{(140 - Age) \times Weight(kg)}{72 \times S_{Cr}(mg / dL)} \times (0.85 \text{ female})$$

- **Left ventricular ejection fraction (LVEF) (%)**
- **Baseline ECG (Normal, Abnormal and not clinically significant, Abnormal and clinically significant, not evaluable)**
- Baseline hypertension history (yes/no)
- Baseline history of ischemic heart disease (yes/no)
- Baseline disease characteristics:
 - **Original ISS stage per IXRS at screening (I or II, III)**
 - **Original ISS stage at baseline (I, II, III)**
 - Revised ISS stage at baseline (I, II, III)
 - MM subtype (**IgG, IgA, IgD, IgE, IgM, None; Kappa, Lambda, Not detectable within each subtype**)

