9.5.1 Analyses of Primary Efficacy Endpoint(s)

The distribution of PFS time including median and quartiles will be summarized descriptively using the Kaplan-Meier method. The corresponding 95% confidence intervals for the median and quartiles will be constructed using the method of [Klein and Moeschberger \(1997\)](#) with log-log transformation. PFS rates at selected landmark time points will be provided and the corresponding 95% confidence intervals will be calculated using the method of [Kalbfleisch and Prentice \(1980\)](#). The duration of the follow-up for PFS will be estimated by reverse Kaplan-Meier method ([Schemper and Smith 1996](#)).

The inferential comparison between treatment groups will use the log-rank test stratified by the randomization stratification factors per IXRS at level of 0.025 (1-sided). The HR

and its 95% CI will be estimated using a Cox proportional hazards model stratified by the same randomization stratification factors.

The primary endpoint of PFS will be analyzed within each of the subgroups listed in [section 4](#). Specifically, to determine whether the treatment effect is consistent across subgroups, the estimate of the hazard ratios (with 95% CI) for PFS between the treatment groups will be provided. Additionally, a treatment-by-subgroup interaction test **may** be provided using a Cox proportional hazards model stratified by the stratification factors.

Piecewise Cox models may be explored given evidence of non-proportional hazards (Collett, 2003). This model will allow estimation of an overall weighted hazard ratio (weights equal to fraction of total events in each interval (Lu & Pajak, 2000)) as well as within interval treatment hazard ratio. Additional analysis may be performed to explore potential sources for non-proportionality by considering baseline prognostic factors and other potential confounding factors.

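### R-ISS stage II is a residual class, so ISS I and ISS III subjects whose stage a missing FISH or LDH result leaves open are labelled stage II

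*SAP*

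**What the plan says.** SAP section 5 (Definitions) calculates R-ISS at baseline from three components. The two outer stages are defined positively:

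- The best stage requires every component to be favourable: "Stage I: ISS stage I and standard risk group by FISH and normal LDH".
- The worst stage requires advanced ISS plus at least one adverse component: "Stage III: ISS stage III and {either high-risk group by FISH or high LDH" (closing brace omitted here).

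The middle stage, by contrast, has no criteria of its own and takes whatever remains: "Stage II: Not R-ISS stage I or III".

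The entry on genetic risk in the same section expects some subjects to have no usable result: the "unknown group consists of subjects who cannot be identified as high-risk nor standard-risk".

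R-ISS is then used in two places:

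- **Baseline table (SAP 9.4).** The row is "Revised ISS stage at baseline (I, II, III"), with no further level. Other rows in that section do have one: frailty has a not-available level, ECG a not-evaluable level, and genetic risk an unknown group.
- **Subgroup analysis (SAP 4.2).** The levels are "revised ISS stage (Stage 1 or 2, Stage 3"), so stages I and II are pooled. SAP 9.5.1 applies the subgroup list to PFS: "The primary endpoint of PFS will be analyzed within each of the subgroups listed in" that part of the SAP. SAP 9.5.2 uses it for ORR, MRD[-]CR and OS.

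On missing data, SAP 8.3 says: "Rules for handling missing data related to endpoints are described in the endpoint definitions or in the description of analyses". R-ISS is not an endpoint, and its definition has no rule for a missing component.

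**The concern.** A class defined as whatever is left over also absorbs subjects who could not be classified. A subject with unknown FISH cannot pass the stage I test, which needs standard-risk FISH. That subject passes the stage III test only if ISS is III and LDH is high. Failing both tests yields stage II, even when the available data do not show stage II.

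Unknown FISH is foreseeable. Protocol 7.3.21.2 ranks FISH behind MRD sequencing for the screening marrow aspirate, so a scant sample goes to MRD first. Missing LDH is less likely, because Protocol 7.3.15 accepts a local screening result when the central one is unavailable. No such fallback exists for FISH.

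Two outputs are at stake. The baseline row would overstate stage II at the expense of I and III. The planned subgroup would hold, in its better-prognosis level, some subjects who belong in Stage 3. For ISS III subjects the error runs in that direction only. The plan is also uneven: SAP 4.2 lists genetic risk as high or standard only, so a subject with unknown FISH has no level there but is given a definite R-ISS level.

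**Working it through.** The plan states no figure on this point, so there is none to reproduce. The check has two parts.

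**1. What the rule does with each missing-data pattern.** For each ISS stage, five patterns have something missing: FISH unknown with LDH normal, high or missing, and LDH missing with FISH standard or high. That gives 3 x 5 = 15 patterns. For each, compare the stage assigned by the SAP section 5 rule with the stages still possible once the missing value is filled in.

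| ISS | FISH | LDH | Rule gives | Possible | Three-level row | Two-level subgroup |
|---|---|---|---|---|---|---|
| I | unknown | normal | II | I or II | open | correct |
| I | unknown | missing | II | I or II | open | correct |
| I | standard | missing | II | I or II | open | correct |
| I | unknown | high | II | II | correct | correct |
| I | high | missing | II | II | correct | correct |
| II | all five patterns | | II | II | correct | correct |
| III | unknown | normal | II | II or III | open | open |
| III | unknown | missing | II | II or III | open | open |
| III | standard | missing | II | II or III | open | open |
| III | unknown | high | III | III | correct | correct |
| III | high | missing | III | III | correct | correct |

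The rule sends 5 + 5 + 3 = 13 of the 15 patterns to stage II and 2 to stage III. On three levels, 3 + 3 = 6 patterns are open. In the pooled subgroup only the 3 ISS III patterns are open, because ISS I and ISS II subjects can never be R-ISS III. These are counts of patterns, not of subjects.

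**2. How many subjects.** From the documents: N = 450 (SAP 3.2). Assumed, because the documents give no rates: 20% ISS III, so 450 x 0.20 = 90 subjects; high LDH share h = 0.20 to 0.30; unknown FISH share u = 0.10 to 0.30; 25% high-risk FISH; all independent, with LDH always available.

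- Undetermined ISS III = 90 x (1 - h) x u
- Truly stage III among them = that number x 0.25
- Labelled Stage 3 = 90 x [h + (1 - h) x (1 - u) x 0.25]
- True stage III = 90 x [h + (1 - h) x 0.25], which is 36.0 at h = 0.20 and 42.75 at h = 0.30

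| u | h | Undetermined | Truly stage III | Labelled Stage 3 | Share of true stage III missed |
|---|---|---|---|---|---|
| 0.10 | 0.20 | 7.2 | 1.8 | 34.2 | 5.0% |
| 0.10 | 0.30 | 6.3 | 1.6 | 41.2 | 3.7% |
| 0.20 | 0.20 | 14.4 | 3.6 | 32.4 | 10.0% |
| 0.20 | 0.30 | 12.6 | 3.2 | 39.6 | 7.4% |
| 0.30 | 0.20 | 21.6 | 5.4 | 30.6 | 15.0% |
| 0.30 | 0.30 | 18.9 | 4.7 | 38.0 | 11.1% |

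The pooled group as labelled has 450 - 41.2 = 408.8 to 450 - 30.6 = 419.4 subjects. The misplaced share of it runs from 1.6/408.8 = 0.4% to 5.4/419.4 = 1.3%.

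**Wider assumptions.** With ISS III 15-30%, unknown FISH 5-30%, normal LDH 80% and 20-40% of unknowns truly high risk, about 3-32 subjects are undetermined and about 0.5-13 are truly stage III. That is 0.1-3.3% of the pooled group and about 2-19% of true stage III.

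**The case against.** The best defence is that R-ISS is said to be calculated from three components, so a sensible programmer would leave it missing when one is absent. The two-level genetic risk list in SAP 4.2 shows that leaving an unknown level off a subgroup list need not mean that unknowns are reassigned. That is a fair reading of intent. But the SAP does not say it and the rule as written gives a different answer, so two programmers could produce different tables.

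The limits on impact stand:

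- A reader might infer that every subject with unknown FISH or missing LDH becomes stage II and contaminates the PFS subgroup. The rules do not support that. ISS III with one known adverse feature is correctly stage III, ISS II is stage II whatever is missing, and pooling I with II keeps every ISS I subject in the right level.
- A reader might also infer that both subgroup hazard ratios are computed on wrong groups. They are not. Everyone labelled Stage 3 has ISS III and a known adverse feature, so is truly Stage 3. No correction can recover the stage III subjects whose data are missing.
- The classification uses baseline data only, so the comparison within each labelled group remains randomized.
- R-ISS is not a stratification factor and has no place in the testing hierarchy of SAP 7.2. The interaction test in SAP 9.5.1 is optional.
- SAP 4.2 allows levels below 10% of an arm to be combined. On the rates above, labelled Stage 3 would be 30.6/450 = 6.8% to 41.2/450 = 9.2%, so the split might not be reported at all.

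**Conclusion.** The point holds in a limited form. The rule gives a definite stage II to six kinds of subject whose stage is open, beside an unknown genetic group that the SAP itself defines. The three-level baseline row is distorted by undetermined subjects from both ISS I and ISS III. In the two-level subgroup the misplacement is confined to ISS III subjects with no known adverse feature and a missing component. On the assumed rates these are about 6-22 subjects, of whom about 2-5 are truly stage III.

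The pooled Stage 1 or 2 estimate and any interaction test would change slightly. The Stage 3 hazard ratio is the same before and after correction, and the primary PFS test and type I error are untouched. The counts rest wholly on assumed ISS, LDH and FISH rates and leave out missing LDH. The classification fault itself needs no assumption. Severity is low.

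**What to change.** In SAP section 5, assign stage II only when the known components establish it, and set R-ISS to Unknown when the available components, including ISS itself, do not determine the stage. Add an Unknown row to the R-ISS entry in SAP 9.4.

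In SAP 4.2, state the handling for the two-level subgroup separately. Keep ISS I and ISS II subjects in Stage 1 or 2 whatever else is missing. Exclude, or show on a separate line, only ISS III subjects with no known adverse feature and a missing component, and subjects with missing ISS.

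A blanket exclusion of Unknown from the subgroup should be avoided. Assuming 40-50% ISS I and 20% unknown FISH, with 20-30% high LDH, it would discard 180 x 0.20 x 0.70 = 25 to 225 x 0.20 x 0.80 = 36 ISS I subjects whose pooled level is certain. It would do so to remove about 13-14 undetermined ISS III subjects.

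The cost is a few lines of SAP text and code. The downside is that a few subjects leave the R-ISS subgroup.
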